## VERSION HISTORY

This statistical analysis plan (SAP) for study ACT16902 is based on the amended protocol 02 dated 21-Jan-2022.

The first participant was enrolled on 10-Jan-2022. This SAP is approved before the first analysis is conducted.

### Major changes in statistical analysis plan

SAP Version	Approval Date	Changes	Rationale	Change from
1	Current version	

• Interim analyses section: removed "without enrollment hold"

• Estimand framework has been added for the primary and main secondary efficacy endpoints.

	

• The enrollment hold was based on a recommendation from the first program-level Data Monitoring Committee (DMC) meeting held on 18 May 2022, to assesses totality of benefit/risk profile based on both efficacy and safety data extracted from clinical database

• To further characterize the antitumor activity effect that will be estimated.

	Amended protocol 02

# 1 INTRODUCTION

## 1.1 STUDY DESIGN

This is a Phase 2, multi-cohort, un-controlled, non-randomized, open-label, multi-center study assessing the antitumor activity and safety of SAR444245 combined with other anticancer therapies in participants with advanced or metastatic gastrointestinal cancer.

This study is developed as a master protocol in order to accelerate the investigation of SAR444245 with various anticancer therapies by identifying early efficacy signals.

The information that is introductory and common to all cohorts is included in the master protocol, and cohort-specific elements are contained in individual substudy protocols. [Table 1](#) presents an overview of substudies and cohorts.

**Table 1 - Overview of study cohorts**

Substudy	Cohort	Study intervention	Disease
01	A	SAR444245 + pembrolizumab	2-3L ESCC - Regardless of CPS Post-PD1/PDL1
02	B1	SAR444245 + pembrolizumab	1-3L GC/GEJ non-MSI-H CPS $\geq 1$ PD-1/PD-L1 Naïve
02	B2	SAR444245 + pembrolizumab	1-3L GC/GEJ non-MSI-H CPS $< 1$ PD-1/PD-L1 Naïve
02	B3	SAR444245 + pembrolizumab	2-4L GC/GEJ non-MSI-H - Regardless of CPS Post-PD1/PDL1
03	C	SAR444245 + pembrolizumab	2-3L post PD1/PDL1 HCC
04	D1	SAR444245 + pembrolizumab	3-6L mCRC non-MSI-H Any RAS
04	D2	SAR444245 + cetuximab	3-6L mCRC non-MSI-H RASwt

ESCC: esophageal squamous cell carcinoma; CPS: combined positive score; GC: gastric cancer; GEJ: gastro-esophageal junction adenocarcinoma, HCC: hepatocellular carcinoma; 1-3L: first to third line; 2-4L: second- to fourth-line; 2-3L: second to third line; 3-6L: third to sixth line; mCRC: metastatic colorectal cancer; MSI-H: high-level microsatellite instability; PD1/PDL1: programmed cell death 1 or programmed cell death-ligand 1; RASwt: RAS wild-type RECIST: response evaluation criteria in solid tumors;

After a screening period of up to 28 days, participants will receive treatment until progressive disease (PD), unacceptable adverse event (AE) or other full permanent discontinuation criteria (described in Section 7 of the master protocol) or completion of Cycle 35 (if applicable).

## 1.2 OBJECTIVE AND ENDPOINTS

**Table 2 - Objectives and endpoints - master protocol**

Objectives	Endpoints
Primary	

 
To determine the antitumor activity of SAR444245 in combination with other anticancer therapies
 
	
 
Objective response rate (ORR) defined as the proportion of participants who have a confirmed complete response (CR) or partial response (PR) determined by Investigator per Response Evaluation Criteria in Solid Tumors (RECIST) 1.1
 

Secondary	

 
To assess the safety of SAR444245 in combination with other anticancer therapies
 
To assess other indicators of antitumor activity
 
	
 
Incidence of treatment emergent adverse events (TEAEs), serious adverse events (SAEs), laboratory abnormalities according to National Cancer Institute Common Terminology Criteria for Adverse Events (NCI CTCAE) V5.0 and American Society for Transplantation and Cellular Therapy (ASTCT) consensus grading
 
Time to response (TTR) defined as the time from the first administration of investigational medicinal product (IMP) to the first tumor assessment at which the overall response was recorded as PR or CR that is subsequently confirmed and determined by Investigator per RECIST 1.1
 
Duration of response (DoR), defined as the time from first documented at which the overall response was recorded as CR or PR that is subsequently confirmed until documented progressive disease (PD) determined by Investigator per RECIST 1.1 or death from any cause, whichever occurs first
 
Clinical benefit rate (CBR) including confirmed CR or PR at any time or stable disease (SD) of at least 6 months determined by Investigator per RECIST 1.1.
 
Progression-free survival (PFS), defined as the time from the date of first IMP administration to the date of the first documented disease progression determined by Investigator as per RECIST 1.1 or death due to any cause, whichever occurs first
 
Plasma concentrations and where applicable PK parameters of SAR444245
 
Incidence of anti-drug antibodies (ADAs) against SAR444245
 

Exploratory	     

Objectives	Endpoints
[REDACTED]	[REDACTED]

**Table 3 - Objectives and endpoints - substudies**

Substudy	Objectives	Endpoints
Secondary		
04 (cohort D2)	
 
• To assess active concentrations of cetuximab when given in combination with SAR444245
 
	
 
• <math>C_{trough}</math> and <math>C_{end\ of\ infusion}</math> of cetuximab
 

Exploratory		
	[REDACTED]	[REDACTED]

### 1.2.1 Estimands

Primary estimand defined for main efficacy endpoints are summarized in below [Table 4](#). More details are provided in [Section 3](#).

**Table 4 - Summary of primary estimand for main endpoints**

Endpoint Category (estimand)	Estimands			
	Endpoint	Population	Intercurrent event(s) (IE) handling strategy	Population-level summary (Analysis and missing data handling)
Primary objective: To determine the antitumor activity of SAR444245 in combination with other anticancer therapies				
Primary endpoint (estimand 1)	Objective Response (OR) (confirmed CR or PR)	Efficacy	
 
While not initiating new anti-cancer therapy (NAT)
 
Regardless of early IMP discontinuation (treatment policy strategy)
 
	ORR, defined as the percentage of the participants with objective response (CR or PR) as best overall response. Confidence interval will be calculated using Clopper Pearson methods.
Secondary objective: To assess other indicators of antitumor activity of SAR444245 in combination with other anticancer therapies				
Secondary endpoint (estimand 2)	DOR	Responders from efficacy population	
 
Had NAT not been initiated (hypothetical strategy)
 
Regardless of early IMP discontinuation (treatment policy strategy)
 
Had two or more consecutive tumor assessments not been missed/unevaluable immediately before documented progression or death (hypothetical strategy)
 
	
The Kaplan Meier estimate and corresponding confidence interval of DOR at specified time points.
 
The quantiles of DOR and corresponding confidence interval from Kaplan Meier method.

Secondary endpoint (estimand 3)	PFS	Efficacy	
 
Had NAT not been initiated (hypothetical strategy)
 
Regardless of early IMP discontinuation (treatment policy strategy)
 
Had two or more consecutive tumor assessments not been missed/unevaluable immediately before documented progression or death (hypothetical strategy)
 
	
The Kaplan Meier estimate and corresponding confidence interval of PFS at specified time points.
 
The quantiles of PFS and corresponding confidence interval from Kaplan Meier method.

## 2 ANALYSIS POPULATIONS

The following populations for analyses are defined.

**Table 5 - Populations for analyses**

Population	Description
Screened	All participants who have given their informed consent.
Enrolled	All participants who have given their informed consent and have been allocated to an intervention (by IRT) regardless of whether the intervention was received or not.
Exposed	All participants who have given their informed consent and received at least one dose (even incomplete) of IMP (SAR444245 or other anticancer therapies).
Population without trial impact (disruption) due to COVID-19	All exposed participants: 

without any critical or major deviation related to COVID-19

and who did not permanently discontinue treatment due to COVID-19

and who did not permanently discontinue study due to COVID-19

Efficacy	All participants from the exposed population with at least one evaluable post-baseline tumor assessment or who permanently discontinued study treatment.
Response-evaluable	All participants from efficacy population with an evaluable baseline and at least one evaluable post-baseline tumor assessments. Participants who died from disease progression before any TA will also be response-evaluable.
Pharmacokinetic (PK)	All participants from exposed population with at least 1 PK concentration available after the first dose of study intervention.
ADA	All participants from exposed population with at least 1 ADA result (positive, negative or inconclusive) after the first dose of study intervention.
Pharmacodynamics (PDy)	All participants from the exposed population with at least 1 PDy parameter assessed after the first dose of study intervention.

Participants exposed to study intervention before or without being enrolled will not be considered enrolled and will not be included in any analysis population. The safety experience of these participants will be reported separately.

For any participant enrolled and treated more than once, only the data associated with the first enrollment will be used in any analysis population. The safety experience associated with any later enrollment will be reported separately

## 3 STATISTICAL ANALYSES

### 3.1 GENERAL CONSIDERATIONS

In general, continuous data will be summarized using the number of observations available, mean, standard deviation (SD), median, minimum, and maximum. Categorical and ordinal data will be summarized using the count and percentage of participants.

The baseline value is defined as the last available value before the first administration of any of the IMPs in combination (refer to [Table 1](#)). For participants enrolled but not treated, the baseline value is defined as the last available value before enrollment.

Unless otherwise specified, analyses will be performed by cohort and overall (if applicable).

All efficacy analyses will be performed on the efficacy population and analyzed by cohort and pooled cohorts (B1 and B2) if relevant.

Objective response rate, as well as all other response-related efficacy endpoints will be primarily derived using the local radiologist's/Investigator's assessment and according to criteria RECIST 1.1.

Central imaging may be done retrospectively if significant activity is observed (See [Section 3.2.3](#) sensitivity analysis).

Confidence intervals will be two-sided 90% CI for efficacy analyses. CI will be used for descriptive purposes only, without inference.

The BOR is defined as the best overall response observed from the date of first IMP until disease progression, death, cut-off date or initiation of subsequent anti-cancer therapy, whichever occurs first.

- A PR or a CR must be confirmed on a second examination done at least 4 weeks apart, in order to confirm the antitumoral response.
- A SD response must be assessed at least 6 weeks after the first IMP administration to be considered as evaluable.

All safety analyses will be performed on the exposed population.

#### *Analysis period*

The analysis period will be divided into 3 segments:

- The **pre-treatment period** is defined as the time from when the participants give informed consent to first administration of the IMP.
- The **on-treatment period** (ie, treatment-emergent (TE) period) is defined as the time from the first administration of IMP up to 30 days after the last administration of IMP.
- The **post-treatment period** is defined as the time from the end of the on-treatment period, ie, 31 days after the last administration of IMP.

## 3.2 PRIMARY ENDPOINT(S) ANALYSIS

### 3.2.1 Definition of endpoint(s)

The primary endpoint is the ORR.

The ORR is defined as the proportion of participants who have a BOR (see [Section 3.1](#)) as confirmed CR or PR.

### 3.2.2 Main analytical approach

The primary endpoint, ORR, will be analyzed with the Estimand 1, introduced in [Section 1.2.1](#), and defined according to the following attributes:

- The endpoint is confirmed objective response (confirmed CR or PR)
- The treatment condition is SAR444245 in combination (refer to [Table 1](#))
- The analysis population is the efficacy population
- Intercurrent events (IE):
  - The new anticancer therapy IE will be handled with the “**while not initiating new anti-cancer therapy**” strategy; confirmed objective response will be assessed based on tumor assessments up to the time of new anticancer therapy.
  - The early IMP discontinuation IE will be handled with the “**treatment policy**” strategy; confirmed objective response will be assessed based on tumor assessments irrespective of IMP discontinuation.
- Population-level summary will include the ORR and confidence interval using the Clopper-Pearson method. In absence of confirmed OR, participants will be considered as non-responders, whatever the reason (including participants with missing or non-evaluable BOR).

### 3.2.3 Sensitivity analysis

Central imaging reading may be done retrospectively if significant activity is observed. ORR may be presented based on central imaging assessment, using the same estimand as for the primary analysis.

### 3.2.4 Supplementary analyses

ORR will be presented for the response-evaluable population.

This supplementary analysis will be provided using an estimand defined according to the following attributes:

- The endpoint is ORR.
- The treatment condition is SAR444245 in combination (refer to [Table 1](#)).

- The analysis population is the response-evaluable population.
- Intercurrent events and their handling strategy will be the same as for ORR estimand defined in [Section 3.2.2](#).
- Population-level summary will be the same as for ORR estimand defined in [Section 3.2.2](#).

In addition, the BOR will be summarized with descriptive statistics.

### **3.3 SECONDARY ENDPOINT(S) ANALYSIS**

The secondary endpoints detailed in this section are the efficacy endpoints. Other secondary endpoints analyses are defined in [Section 3.6](#) (safety), [Section 3.7.1](#) (PK) and [Section 3.7.1.2](#) (immunogenicity).

#### **3.3.1 Efficacy secondary endpoint(s)**

##### **3.3.1.1 *Definition of endpoint(s)***

The time to response is defined as the time from the first administration of IMP to the first tumor assessment at which the overall response was recorded as PR or CR that is subsequently confirmed.

The duration of response (DOR) will be defined as the time from the first tumor assessment at which the overall response was recorded as CR or PR that is subsequently confirmed until documented PD before the initiation of any subsequent anti-cancer therapy or death due to any cause, whichever occurs first.

The clinical benefit rate (CBR) is defined as the proportion of participants with clinical benefit: confirmed CR or PR as BOR, or SD lasting at least 6 months (overall response recorded as SD at 6 months, ie, 26 weeks or later from first IMP intake, allowing for the  $\pm 7$  days visit window for tumor assessment scheduled at 27 weeks).

The progression-free survival (PFS) is defined as the time from the date of first IMP administration to the date of the first documentation of objective PD, or death due to any cause, whichever occurs first.

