**Table 6 - Censoring rules for DOR and PFS**

Situation	Date of progression or censoring	Outcome	Category
No baseline tumor assessments a	Date of first treatment intake	Censored	No baseline tumor assessments
No evaluable b post-baseline tumor assessments a	Date of first treatment intake	Censored	No evaluable post-baseline tumor assessments
Progression documented at or between scheduled visits	Date of the first tumor assessment documenting progression	Event	Documented progression
New anticancer treatment before documented progression	Date of the last evaluable tumor assessment before new treatment	Censored	New anticancer treatment
Death prior to the first planned post-baseline tumor assessment a	Date of death	Event	Death

Situation	Date of progression or censoring	Outcome	Category
Death at or between scheduled visits	Date of death	Event	Death
Death or documented progression immediately after two c or more missed or non-evaluable tumor assessments	Date of the last evaluable tumor assessment documenting no progression	Censored	Death or progression after two or more missed/unevaluable tumor assessments
Alive and no documented progression	Date of the last evaluable tumor assessment	Censored	Alive without documented progression

[figure not shown]
*a* Not applicable for DOR.  
*b* Evaluable TA means an evaluation different from non-evaluable.  
*c* Two consecutive tumor assessments are considered as missed/non-evaluable if the duration between two consecutive tumor assessments done (non-missing) and evaluable is strictly longer than 20 weeks.

[figure not shown]
The clinical benefit rate will be summarized using the same estimand as for the primary endpoint.

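### Read literally, the 26-week SD rule for clinical benefit fails a participant whose only non-progression scans from week 26 on are unconfirmed PR or CR

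*SAP*

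**What the plan says.** SAP Section 3.3.1.1 gives two routes to clinical benefit: "confirmed CR or PR as BOR, or SD lasting at least 6 months". A parenthesis turns the second route into a rule: "overall response recorded as SD at 6 months, ie, 26 weeks or later from first IMP intake". It explains the 26-week limit by the 7-day "days visit window for tumor assessment scheduled at 27 weeks".

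The same section defines time to response by the "first tumor assessment at which the overall response was recorded as PR or CR that is subsequently confirmed". There, the overall response being recorded plainly means the result of a single assessment, not the best overall response (BOR).

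Section 3.1 adds two rules for BOR: "A PR or a CR must be confirmed on a second examination done at least 4 weeks apart", and "A SD response must be assessed at least 6 weeks after the first IMP administration to be considered as evaluable". Neither says how a PR or CR that is never confirmed is to be classed.

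Table 2 describes the endpoint more briefly: "Clinical benefit rate (CBR) including confirmed CR or PR at any time or stable disease (SD) of at least 6 months". The sentence after Table 6 reads "The clinical benefit rate will be summarized using the same estimand as for the primary endpoint". That estimand (Section 3.2.2) treats the absence of a confirmed response as non-response, whatever the reason.

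**The concern.** The evident purpose of the second route is to credit participants who stay free of progression for about 6 months without a confirmed response. The rule as written asks for something narrower: an assessment at or after week 26 that carries the label SD. A PR at that assessment that is never confirmed meets neither route, although the tumour result is better than SD. The rule can therefore rank a better result below a worse one.

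Two things are at stake. CBR can be understated, and never overstated, relative to a rule that accepts SD or better. In addition, one programmer who codes the parenthesis and another who codes the phrase before it could report different CBRs from the same data.

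**Working it through.** **Inputs.** The 26-week limit, the week-27 scan and its 7-day window come from SAP Section 3.3.1.1. The confirmation rule and the 90% confidence level come from Section 3.1. The cohort size of 40 comes from Section 4, and the cut-offs from Section 3.8. Scans every 9 weeks are an assumption, because the SAP names only week 27. The assumption fits 27 = 3 × 9. It also fits the 20-week gap in Table 6, footnote c, since 2 × 9 weeks + 2 × 7 days = 20 weeks.

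**The plan's own figures.** The time limit reproduces: 27 × 7 − 7 = 182 days = 26 × 7. Six months is 6 × 30.4375 = 182.6 days. All seven rows of Table 14 reproduce with the exact 90% Clopper-Pearson interval at N = 40, for example 8/40 = 20% (10.4–33.2).

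**Two rules compared.**
- Literal rule: confirmed CR or PR, or any assessment at week ≥ 26 equal to SD.
- SD-or-better rule: confirmed CR or PR, or any assessment at week ≥ 26 equal to SD, PR or CR.

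None of the sequences below contains a confirmed response.

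| Assessments (week) | Literal | SD or better |
|---|---|---|
| SD 9, SD 18, SD 27, PD 36 | benefit | benefit |
| SD 9, SD 18, PR 27, PD 36 | **no benefit** | benefit |
| SD 9, SD 18, PR 27, no later scan | **no benefit** | benefit |
| SD 9, SD 18, PR 27, SD 36, PD 45 | benefit | benefit |
| SD 9, SD 18, SD 27, PR 36, PD 45 | benefit | benefit |
| SD 9, PR 18, SD 27, PD 36 | benefit | benefit |

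Rows 1 and 2 differ only at week 27, where the better result receives the worse classification. Rows 4 to 6 show the limit of the problem: one SD record at or after week 26 is enough. A PR at both weeks 18 and 27 is also safe, because the two are more than 4 weeks apart and the response is confirmed.

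**Direction.** Every participant who passes the literal rule also passes the SD-or-better rule, so the literal CBR can only be equal or lower.

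**Size.** One participant is 1/40 = 2.5 points. The number affected is not in the SAP. If it were 0 to 2 per cohort (an assumption), the shift would be 0 to 5 points. Starting from an assumed 8/40 under the literal rule:

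| Reclassified | CBR | 90% CI |
|---|---|---|
| 0 | 8/40 = 20.0% | 10.4–33.2 |
| 1 | 9/40 = 22.5% | 12.3–36.0 |
| 2 | 10/40 = 25.0% | 14.2–38.7 |

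**Cut-off.** Secondary endpoints are analysed 18 months after the last participant enters the cohort: 18 × 30.4375 / 7 = 78 weeks. A participant still being scanned then, whose first PR is at the last scan, will normally have had SD at week 27 and later, and so counts. Even at the primary cut-off of about 9 months (9 × 30.4375 / 7 = 39 weeks), the last scan on the assumed schedule is week 36, after the week-27 scan.

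**The case against.** The strongest reply is that the governing phrase is SD of at least 6 months, and that the parenthesis only explains timing. On that view, a participant with SD at weeks 9 and 18 and no confirmed response has SD as BOR, and the SD lasts until PD. Section 3.1 also derives response endpoints under RECIST 1.1, which may settle how an unconfirmed PR is classed. This reading is reasonable, and a programmer might adopt it. But the SAP does not state it, and the parenthesis, which is the part that can be programmed, names SD alone. The generous reading is a reason to write the rule down, not a reason to leave it.

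The second reply is that the case is rare and decides nothing. That stands. With scans on schedule, it needs a first PR at about week 27 with neither confirmation nor a later SD. A missed or non-evaluable week-27 scan could widen it slightly. One case moves CBR by 2.5 points, against an interval 33.2 − 10.4 = 22.8 points wide at 8/40. Section 3.1 makes the intervals descriptive, futility in Section 3.8 uses ORR, and PFS and BOR are reported separately.

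A reader might infer that any unconfirmed PR after 26 weeks is scored as a failure, or that a first PR at the last scan before cut-off generally is. The documents do not support either. The words allowing a record at 26 weeks or later rescue anyone with another SD in that period, and the 18-month cut-off normally leaves one. The same holds for a first PR at week 36 just before new therapy, if week 27 was SD.

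**Conclusion.** The point holds in a narrow form. Under the literal rule in Section 3.3.1.1, a participant without a confirmed response, whose only non-progression assessments from week 26 on are unconfirmed PR or CR, is scored as no benefit. The same participant with SD at that assessment would be scored as benefit. No other part of the SAP closes this gap.

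The effect runs one way and costs 2.5 CBR points per case at N = 40. The number of cases cannot be derived from the SAP and is probably small; zero is plausible in a given cohort. A reader might take this as evidence of a material bias in CBR, but that would rest on an assumed count. The 26-week limit itself is sound. This is a minor correction to a descriptive secondary endpoint.

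**What to change.** In Section 3.3.1.1, replace the SD condition in the parenthesis with:

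> *at least one overall response of SD or better (including unconfirmed CR/PR) at 26 weeks or later from first IMP intake, before PD and before new anticancer therapy*

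Keep the existing 7-day window wording for the week-27 scan. The limits at PD and new therapy partly repeat the BOR window in Section 3.1 and the primary estimand, but stating them here makes the rule complete in one place.

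The cost is one sentence in the SAP and one line in the derivation, with no new data and no change to ORR, PFS or the futility rule. It should be settled before CBR is derived.
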